7.3.3 Safety analyses

DLTs will be tabulated for each dose cohort in phase Ib (escalation). The tabulation will be done in two ways:

Trial Protocol Version 12

Page 98 of 241

Proprietary confidential information. © 2022 Boehringer Ingelheim International GmbH or one or more of its affiliated companies. All rights reserved.

- DLTs with onset in the first treatment course, and
- All DLTs regardless of treatment course at onset

The MTD analysis is defined in Section 5.2.4.

Adverse events will be graded according to CTCAE, Version 4.03 (R10-4848). Key safety measures will include:

- Events leading to dose reduction or permanent treatment discontinuation
- The overall incidence and intensity of AEs, as well as seriousness and relatedness of adverse events to treatment

[figure not shown]
Other safety-relevant assessments including those involving ECG, and ECOG score, will be described with respect to possible changes compared to baseline values. Further details on the analysis of ECG data will be specified in the TSAP.

7.3.4 **Interim analyses**

No formal interim analysis is planned for efficacy. In the phase Ib escalation, the study team will continuously monitor and assess safety data to ensure patients' safety, as well as to determine the dose for the exploratory expansion cohort and phase II. If considered necessary, as soon as the MTD and/or the recommended phase II dose is determined, an evaluation of the safety and efficacy aspects will be performed via a snapshot of the database. Results of this evaluation will be documented and stored.

Continuous monitoring of safety data for phase Ib expansion cohort will be done by the BI study team and trial investigators and phase II will be done by an internal DMC to ensure a benefit risk assessment during the DMC meetings. During regular meetings, the committee may examine the efficacy data in order to completely assess the benefit risk advantage of BI 836845 in combination with enzalutamide.

The results of the phase Ib expansion cohort and the phase II will be analysed separately.

Boehringer Ingelheim BI Trial No.: 1280.8 Doc. No.: c02304008-15

Trial Protocol Version 12

06 Jun 2022

Page 99 of 241

Proprietary confidential information. © 2022 Boehringer Ingelheim International GmbH or one or more of its affiliated companies. All rights reserved.

7.4 HANDLING OF MISSING DATA

In general, missing data will not be imputed. Further details for handling of missing PSA values will be specified in the TSAP.

See section 3.3.5 for replacement of patients.

For PFS, every effort will be made to obtain date of progression for patients known to have progressed. Detailed censoring rules will be specified in the TSAP.

BI Trial No.: 1280.8 Doc. No.: c02304008-15

Trial Protocol Version 12 Proprietary confidential information. © 2022 Boehringer Ingelheim International GmbH or one or more of its affiliated companies. All rights reserved.

Page 100 of 241

For partial or missing AE onset and/or end dates, BI internal rules will be followed for

imputation (see Reference Document 001-MCG-156 RD01 "Handling of missing and

incomplete AE dates").

7.5 RANDOMISATION

No randomisation is needed for phase Ib. Patients will be assigned sequentially to the dose cohort at the time for the escalation part, and to the MTD and/or recommended phase II dose.

In phase II, patients will be randomised in a 1:1 ratio to each of the two treatment groups.

Treatment assignment will be centrally managed by means of a third-party phone/web-based randomisation during the screening phase. This will involve the use of an interactive response technology (IRT i.e. Interactive Voice Response System [IVRS]/Interactive Web Response System [IWRS]). Boehringer Ingelheim will arrange the randomisation. A randomisation list will be generated using a validated pseudo-random number generator, yielding reproducible and non-predictable results.

7.6 DETERMINATION OF SAMPLE SIZE

Phase Ib escalation follows a 3+3 design to determine the MTD and/or recommended phase II dose of BI 836845 in combination with enzalutamide. Approximately 9-12 patients may be assessed. Assuming two cohorts are needed to determine the MTD, 3-6 patients may be treated in the first cohort, followed by 3-6 patients in the second cohort.

The phase Ib exploratory expansion cohort consists of one cohort treated at the MTD and/or recommended phase II dose. In this cohort, approximately 25 additional patients will be

Page 101 of 241

Doc. No.: c02304008-15

Proprietary confidential information. © 2022 Boehringer Ingelheim International GmbH or one or more of its affiliated companies. All rights reserved.

treated to ensure 21 evaluable patients. Assuming a PSA response rate of 30% (P14-02928, see Arm B2), a sample size of evaluable 21 patients leads to a probability of about 80% of observing at least 5 patients with a PSA response (as shown in Table 7.6: 1 below).

If the true PSA response rate is less i.e. 25%, then the probability of observing at least 5 PSA responses is 63%. If the true PSA response rate is higher i.e. 35%, then the probability of observing at least 5 PSA responses is 91%. A probability of 80% was seen as sufficient, leading to the chosen sample size of 21 evaluable patients. In the phase Ib expansion part of the study an evaluable patient is defined as a patient where data for the assessments of the primary endpoint is available.

The probability of a false positive signal is also sufficiently small given a sample size of 21 evaluable patients. For example, the probability of observing 5 PSA responses if the true PSA response rate is 5% is less than 0.5%.

Table 7.6: 1 Probability of observing at least x events, given a true PSA response rate and sample size

True	Number of	Probability of observing at least				
PSA response Rate	patients in cohort	3 events*	4 events*	5 events*	6 events*	7 events*
0.25	18	0.8647	0.6943	0.4813	0.2825	0.1390
	21	0.9255	0.8083	0.6326	0.4334	0.2564
	24	0.9602	0.8850	0.7534	0.5778	0.3926
0.30	18	0.9400	0.8354	0.6673	0.4656	0.2783
	21	0.9729	0.9144	0.8016	0.6373	0.4495
	24	0.9881	0.9576	0.8889	0.7712	0.6114
0.35	18	0.9764	0.9217	0.8114	0.6450	0.4509
	21	0.9914	0.9669	0.9076	0.7991	0.6433
	24	0.9970	0.9867	0.9578	0.8956	0.7894
0.05	18	0.0581	0.0109	0.0015	0.0002	0.0000
	21	0.0849	0.0189	0.0032	0.0004	0.0000
	24	0.1159	0.0298	0.0060	0.0010	0.0001

^{*} event = decline in PSA > 50% from baseline.

The phase II of the trial is intended to provide evidence that will allow informed decision making during the next stages of development. The phase II is therefore sized such that, if the true hazard ratio of BI 836845 in combination with enzalutamide versus enzalutamide alone was 0.65, the probability of observing a small hazard ratio is sufficiently large. Similarly, if the true hazard ratio was 1, the probability of observing a small hazard ratio should be sufficiently small. Table 7.6: 2 displays the probability of observing a hazard ratio less than a threshold X, given a true hazard ratio and a pre-specified number of events.

Page 102 of 241

Doc. No.: c02304008-15

Proprietary confidential information. © 2022 Boehringer Ingelheim International GmbH or one or more of its affiliated companies. All rights reserved.

Table 7.6: 2 Probability of observing a hazard ratio $\leq X$, given a true hazard ratio and a pre-specified number of events

True hazard ratio	Number of PFS	Probability ² of observing a hazard ratio $\leq X$			
(Arm A / Arm B) ¹	events ³	X = 0.7	X = 0.8	X = 0.9	X = 1.0
0.65	40	0.59	0.74	0.85	0.91
	50	0.60	0.77	0.88	0.94
	60	0.61	0.79	0.90	0.95
	70	0.62	0.81	0.91	0.96
0.67	40	0.56	0.71	0.82	0.90
	50	0.56	0.73	0.85	0.92
	60	0.57	0.75	0.87	0.94
	70	0.57	0.77	0.89	0.95
0.70	40	0.5	0.66	0.79	0.87
	50	0.50	0.68	0.81	0.90
	60	0.50	0.70	0.83	0.92
	70	0.50	0.71	0.85	0.93
1.0	40	0.13	0.24	0.37	0.5
	50	0.10	0.22	0.35	0.50
	60	0.08	0.19	0.34	0.50
	70	0.07	0.18	0.33	0.50

¹ Arm A = BI 836845 in combination with enzalutamide, Arm B = enzalutamide alone.

Assuming the true hazard ratio is between 0.65 and 0.70, and given 60 events, the probability of observing a hazard ratio of less than 0.8 is sufficiently high, between 0.70 and 0.79. In comparison, if the true hazard ratio is 1.0 (i.e. no treatment effect) and given 60 events, the probability of observing a hazard ratio of less than 0.8 is sufficiently low at 0.19.

Due to the inherent difficulties determining radiographic progression in this indication, a central imaging unit is employed to interpret the radiographic images and obtain an independent tumour assessment in addition to the investigator's assessment. However, due to these difficulties, there is potentially a high discordance rate between the independent review and the investigators (fewer independent review events compared to investigator assessed events). From Table 7.6: 2 it can be seen that having a discordance rate of going up to 33% – leaving potentially only 40 independent review events – still gives a probability of between 0.66 and 0.74 (corresponding true underling HR of between 0.65 and 0.70) of observing a HR of less than 0.8 in the evaluation of the independent review as well. If the true underlying HR should be 1.0, then the probability of observing a HR of 0.8 is still sufficiently low with 0.24.

Due to the patients' advanced condition and previous treatment regiments obtained before joining this study, the estimated median PFS time in the enzalutamide arm is around 3 months, and between 4.3-4.6 months in the combination arm of BI 836845 + enzalutamide.

² Calculated based on the approximate normal distribution of the estimated log hazard ratio, i.e. assuming the log hazard ratio is normally distributed with mean log(true hazard ratio), and variance (4 / number of PFS events) (R10-4988).

³ Note that 70 events out of 80 patients can only be seen if the number of permanently censored patients is very low.

Proprietary confidential information. © 2022 Boehringer Ingelheim International GmbH or one or more of its affiliated companies. All rights reserved.

Assuming recruitment rates of 10-13 patients per month for a period of A months, the percentage of observed PFS events relative to sample size is a function of study duration T:

$$\frac{1}{2} \left[\left(1 - \frac{e^{-\lambda_1(T-A)} - e^{-\lambda_1 T}}{A\lambda_1} \right) + \left(1 - \frac{e^{-\lambda_2(T-A)} - e^{-\lambda_2 T}}{A\lambda_2} \right) \right].$$

where λ_1 =0.151 and λ_2 =0.231 are the parameters of exponential distribution assuming median PFS of 4.6 months for BI 836845 in combination with enzalutamide and 3 months for emzalutamide alone. Based on the formula above, and taking multiple parameter combinations into consideration, the study duration until the required numbers of events are obtained is estimated to be between 17-23 months. Therefore, the primary analysis is targeted when 60 PFS events by investigator's assessment are observed or 23 months after the first patient was randomized in the phase II part.

Table 7.6: 3 Study duration until targeted number of 60 PFS events from 80 randomised patients are observed for different possible underlying scenarios

Median PFS	Median PFS	Rate of	Accrual	Expected trial duration to
Enzalutamide	BI 836845 +	permanently		reach the expected
alone	Enzalutamide	censored	period	number of PFS events
[months]	[months]	patients*	[months]	[months]
3	4.3	20%	9	19.9
3	4.6	20%	9	20.6
3	4.3	15%	9	16.4
3	4.6	15%	9	16.9
3	4.3	20%	12	21.9
3	4.6	20%	12	22.5
3	4.3	15%	12	18.4
3	4.6	15%	12	18.8

^{*} Percentage of patients that leave the study without a PFS event

Proprietary confidential information. © 2022 Boehringer Ingelheim International GmbH or one or more of its affiliated companies. All rights reserved.

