3.3 SELECTION OF TRIAL POPULATION

A total of up to approximately 120 patients may be recruited into the study. Approximately 9-12 patients will be entered into the phase Ib tolerability and safety phase of the study (escalation part) to ensure the safety of the combination therapy and determine the MTD and/or recommended phase II dose (RP2D). For the exploratory expansion cohort approximately 25 patients will be treated with BI 836845 at the MTD, and/or recommended phase II dose (RP2D) in combination with enzalutamide.

In phase II of the study, 80 patients will be randomised onto one of the two study arms, with 40 patients randomised to each arm (Arm A=40, Arm B=40).

The Phase Ib escalation part of the study will be performed in 4 or more centres. The Phase Ib expansion part of the study will be performed in 8 or more centres. The Phase II of the study will be performed in 25-30 centres globally.

A log of all patients included into the study (i.e. having given informed consent) will be maintained in the ISF at the investigational site irrespective of whether they have been treated with investigational drug or not.

Page 39 of 241

Proprietary confidential information. © 2022 Boehringer Ingelheim International GmbH or one or more of its affiliated companies. All rights reserved.

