	Due to the inherent difficulties determiningobserving a HR of 0.8 is still sufficiently low with 0.19 Due to the patients' advanced condition and previous treatmentin the combination arm of BI836845 + enzalutamide. Assuming recruitment rates of 10-13 patients per month for a period of A monthsafter the first patient was randomized in the phase II part. Table 7.6:3 was added.
Rationale for change	Table 7.6: 2 has been updated to take into account more assumptions with regard to true HR. Details have been added to the descriptions to account for potential discrepancies between investigator and independent review assessment. As there is now the possibility of not waiting for the 90 events, it has also been described in this section how the minimum duration of the trial has been calculated. Table 7.6:3 has been added to provide examples of expected time to reach primary endpoint of 90
	events.
Section to be changed	10.6 Appendix: Examples of CYP 3A4 and CYP2C8 INHIBITORS, INDUCERS AND CYP3A4 substrates
Description of change	The list has been updated to include examples of CYP2C8 inhibitors and inducers and CYP3A4 inhibitors and inducers.
Rationale for change	Updated based on new language in section 4.2.2 of protocol.
Section to be changed	

Doc. No.: c02304008-15

Description of change	Appendix added
Rationale for change	To provide real examples of bone progressions according to PCWG2 guidelines

Number of global amendment	5
Date of CTP revision	19 November 2015
EudraCT number	2013-004011-41
BI Trial number	1280.8
BI Investigational Product(s)	BI 836845

Title of protocol	A Phase Ib/II, Multicentre, Open Label, Randomised Study of BI 836845 in Combination With Enzalutamide, versus Enzalutamide alone, in Metastatic Castration-Resistant Prostate Cancer (CRPC) Following Disease Progression on
	Docetaxel-Based Chemotherapy and Abiraterone
	lea .
To be implemented only after approval of the IRB/IEC/Competent	$\overline{\mathbf{X}}$
Authorities	
To be implemented immediately in order to eliminate hazard – IRB / IEC / Competent	
Authority to be notified of change with request for approval	
Can be implemented without IRB/IEC/ Competent Authority approval as changes involve logistical or administrative aspects only	
Section to be changed	Protocol Synopsis: Number of patients:
Description of change	At least 21 patients changed to approximately 25 patients

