	sufficiently high, between 0.84 and 0.75. In
	comparison, if the true hazard ratio is 1.0 (i.e. no
	treatment effect) and given 90 events, the
	probability of observing a hazard ratio of less
	than 0.8 is sufficiently low at 0.14.
	than 0.0 is sufficiently low at 0.14.
	()
	From Table 7.6: 2 it can be seen that having a
	discordance rate of going up to 33% – leaving potentially only 60 independent review events – still gives a probability of between 0.79 and 0.70 (corresponding true underling HR of between 0.65 and 0.70) of observing a HR of less than 0.8 in the evaluation of the independent review as well. If the true underlying HR should be 1.0, then the probability of observing a HR of 0.8 is still sufficiently low with 0.19.
	()
	Therefore, the primary analysis is targeted when 90 PFS events by investigator's assessment are observed or 23 months after the first patient was randomized in the phase II part.
	To:
	Assuming the true hazard ratio is between 0.65 and 0.70, and given 60 events, the probability of observing a hazard ratio of less than 0.8 is sufficiently high, between 0.70 and 0.79 . In
	comparison, if the true hazard ratio is 1.0 (i.e. no
	treatment effect) and given 60 events, the

	probability of observing a hazard ratio of less than 0.8 is sufficiently low at 0.19 .
	()
	From Table 7.6: 2 it can be seen that having a discordance rate of going up to 33% – leaving potentially only 40 independent review events – still gives a probability of between 0.66 and 0.74 (corresponding true underling HR of between 0.65 and 0.70) of observing a HR of less than 0.8 in the evaluation of the independent review as well. If the true underlying HR should be 1.0, then the probability of observing a HR of 0.8 is still sufficiently low with 0.24.
	()
	Therefore, the primary analysis is targeted when 60 PFS events by investigator's assessment are observed or 23 months after the first patient was randomized in the phase II part.
Rationale for change	Text updated according to new statistical estimations, a project level decision, and sample size calculations.
Section to be abanged	Table 7.6:3
Description of change	Change of table title and column title from
	Study duration until targeted number of 90 PFS events from 120 randomised patients are observed for different possible underlying scenarios And Drop out rate

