4.4 CLARIFICATIONS TO THE PRIMARY ANALYSIS

The protocol (Section 7.3.1) mentions that the primary analysis will be conducted approximately 23 months after first patient was randomized in phase II part, in case 60 Progression Free Survival (PFS) events are not reached. According to the Table 7.6:3 from the protocol, the calculated duration was actually 22.5 months. The impact of this difference in terms of PFS events is negligible, and it has therefore been decided and agreed to perform this primary analysis 22.5 months after first patient randomized, in case 60 events are not reached.

The protocol (Section 4.1.5.1) states as well that "the BI study team will be blinded for the aggregated phase II data at the treatment level until the trial database lock". The trial and project team clarified and agreed that it is meant until the trial database lock (DBL) of the primary analysis. Indeed, there is no additional blinded team planned for this trial and almost all patients will be off-treatment at that time. The BI study team will therefore be completely unblinded after DBL of the primary analysis.

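### Does the 10-13 per month recruitment rate, which does not fit the accrual periods in Table 7.6:3, undermine the 22.5-month fallback for the primary analysis?

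*Protocol*

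**What the plan says.** Protocol 3.3 fixes the size of the randomised part: "In phase II of the study, 80 patients will be randomised onto one of the two study arms". Protocol 7.6 then gives the accrual assumption, "Assuming recruitment rates of 10-13 patients per month for a period of A months, the percentage of observed PFS events relative to sample size", and a formula for that share as a function of study duration T and accrual period A. Median PFS is 3 months on enzalutamide alone and 4.3 to 4.6 months on the combination.

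Table 7.6:3 is titled "Study duration until targeted number of 60 PFS events from 80 randomised patients are observed for different possible underlying scenarios". It varies the combination median (4.3 or 4.6 months), the permanently censored share (15% or 20%) and the accrual period (9 or 12 months). Its durations run from 16.4 to 22.5 months. The text beneath the formula summarises the range as 17-23 months and sets the primary analysis at 60 investigator-assessed events or 23 months after the first phase II randomisation.

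SAP 4.4 moves that time limit by half a month: "According to the Table 7.6:3 from the protocol, the calculated duration was actually 22.5 months". It keeps the 60-event trigger and calls the effect of the half month negligible.

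**The concern.** The A in the rate sentence, the A in the formula and the accrual column of the table are the same quantity. For 80 patients, 10-13 per month and 9 or 12 months cannot both be right, and no slower rate or ramp-up is stated anywhere. The figure of 22.5 months appears in one row only (combination median 4.6, 20% censored, 12 months' accrual), and that row implies a rate the protocol does not give. If the table were wrong, the pre-specified time limit for the primary analysis would rest on a faulty calculation.

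A second point adds to the doubt. The printed formula has no term for permanent censoring although the table varies it, so a reader who applies the formula as printed cannot recover the table.

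**Working it through.** **Inputs.** N = 80, allocated 1:1 (Protocol 3.3 and 7.5). Target 60 events, so 60/80 = 0.75. Medians 3 and 4.3 or 4.6 months, so λ = ln 2/median = 0.231 and 0.161 or 0.151. Permanently censored share c = 15% or 20%. A = 9 or 12 months (all Protocol 7.6).

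**Accrual.**
- Stated rate: 80/13 = 6.15 months; 80/10 = 8.0 months.
- Table: 80/9 = 8.9 per month; 80/12 = 6.7 per month.

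**Formula.** For each arm, F(T) = 1 − [exp(−λ(T − A)) − exp(−λT)]/(Aλ). The two arms are averaged. Solve (1 − c) × average F(T) = 0.75 for T.

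**The row behind 22.5 months** (A = 12, T = 22.5, medians 4.6 and 3, c = 20%).
- Combination: 1 − (0.2055 − 0.0337)/1.808 = 0.905.
- Control: 1 − (0.0884 − 0.0055)/2.773 = 0.970.
- Average 0.9375; times 0.80 = 0.750; times 80 = 60.0 events.

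**All rows, and the same scenarios at the stated rates** (months to 60 events):

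| Combination median | c | Table, A = 9 | Recomputed | Table, A = 12 | Recomputed | A = 6.15 | A = 8.0 |
|---|---|---|---|---|---|---|---|
| 4.3 | 20% | 19.9 | 19.90 | 21.9 | 21.86 | 18.15 | 19.27 |
| 4.6 | 20% | 20.6 | 20.56 | 22.5 | 22.50 | 18.83 | 19.94 |
| 4.3 | 15% | 16.4 | 16.42 | 18.4 | 18.39 | 14.67 | 15.79 |
| 4.6 | 15% | 16.9 | 16.88 | 18.8 | 18.82 | 15.14 | 16.25 |

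All eight rows agree with the table, so it was computed with 9 and 12 months and with the (1 − c) factor. Without that factor the formula reaches 75% at 12.4 to 12.6 months (A = 9) and 14.3 to 14.6 months (A = 12), which matches no row. At 10-13 per month the range is 14.7 to 19.9 months.

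**Expected events at the time limit** (80 × (1 − c) × average F):
- At 22.5 months, A = 6.15 to 8.0: 61.4 to 62.2 with 20% censored; 65.2 to 66.0 with 15%.
- A = 12, median 4.6, 20% censored: 60.0 at 22.5 months and 60.3 at 23 months, so the SAP's half month costs about 0.3 of an event.
- A = 12, 20% censored, at 19.9 months: 57.8 to 58.3.

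**Could the fallback still be used at the stated rates?** Yes. With 20% censored at random per patient, the binomial chance (n = 80) of fewer than 60 events by 22.5 months is about 23-30%. With 15% censored it is about 3-5%.

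**The case for a change.** The strongest case for acting is that the time limit is a pre-specified trigger. The SAP tightened it on the table's authority alone, and that authority rests on an accrual period the protocol's only rate sentence rules out. The table is headed as a set of possible scenarios and the text mentions several parameter combinations, but no row uses an accrual period that the stated rate allows. If slower accrual was meant, the rate sentence is wrong. A correction would cost only a few words.

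The inconsistency stands, and so does the missing factor in the formula. The step from there to a defect in the trigger does not. SAP 4.4 relies on the table, not on the rate, and the table is right for the accrual periods it prints. Rebuilding it at 10-13 per month would give a longest scenario of 19.9 months. That would remove the support for 22.5 months rather than improve it, and a limit moved to 19.9 months would leave about 58 expected events if accrual took 12 months with 20% censored. Nor can the fallback be dismissed as never needed at the stated rates, since the chance of falling short by 22.5 months is material when 20% are censored. The existing limit is therefore a reasonable one to keep under either reading.

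**Conclusion.** The recruitment phrase is a clerical slip in the planning text. About 6.7 to 8.9 patients per month is what the table assumes for 80 patients, and a reader can recover this from the printed accrual column. The missing (1 − c) factor can likewise be recovered from the table's censoring column and its footnote. The discrepancy is about 1.7 months on the 9-month rows (9 against 6.15) and 2.6 months on the 12-month rows (12 against 8.0), always in the direction of a later time limit.

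No change to the plan follows. The primary analysis is triggered by 60 events, with time only as a fallback. The number of patients, the event target, the probabilities in Table 7.6:2 and the 22.5-month limit stay as they are whichever accrual figure is taken as intended. Protocol 7.2 bases inference on the size of the observed difference rather than on a formal test, so no error rate depends on the forecast either. The durations rest on the protocol's own assumptions of exponential PFS and uniform accrual. The probabilities of falling short also assume that permanent censoring strikes patients independently.
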